8.2.2.1. Statistical Analysis

The number and percent of subjects meeting each criterion and the overall criteria will be summarized by treatment group and visit. All data will be listed showing when subjects failed the criteria and which criterion they failed.

8.2.3. Time to First Disease Flare after Clinical Remission

Only subjects who achieve clinical remission will be included in this analysis. To address this endpoint, the following definitions will be used:

Clinical remission: A similar approach as for the primary endpoint will be used: Clinical remission is defined as absence of clinical signs and symptoms of GCA

A subject in clinical remission is a subject that does not have any signs and symptoms, which is also determined by a lack of flare for the subject. If a subject does have a flare, they will have one or more signs and symptoms, and therefore are not considered as being in clinical remission.

The following rule will be used to assess Clinical remission:

“Has the patient flared since their last visit?” should be answered “No” at a given visit. Clinical remission can occur at any visit between Baseline and Week 52.

Time to first disease flare after clinical remission is the time (days) from the first clinical remission date to the earliest disease flare date:

Disease flare after clinical remission: Date of first disease flare (as collected in the assessment of GCA disease activity) after clinical remission as defined above.

Time to first disease flare (days) = Date of disease flare date – Date of clinical remission + 1 day

Subjects without disease flare at the time of analysis and who have completed the Week 52 visit will be censored at the date of the Week 52 visit. Subjects without disease flare at the time of analysis withdrew from the study or die will be censored at the date of early withdrawal or death. Data observed at or prior to the baseline visit will not be included in this analysis. Handling of missing data in the clinical remission component will be as described in [Section 4.6.2.1](#).

8.2.3.1. Statistical Analysis

A Kaplan-Meier analysis will be summarized. The number of subject achieving clinical remission, as well as the number of subjects with a disease flare and the number of subjects censored with their censoring reasons will be summarized. 25th percentile, median and 75th percentile time to first flare will be summarized in days for each treatment group.

A listing of details of flares will be produced (date of first clinical remission, date of first flare after clinical remission, time from clinical remission to flare).

8.2.4. Number of Disease Flares per Subject over Time

The cumulative number of disease flares is the total number of flares from first SC IP to the Week 52 visit, as collected in the “Clinical Assessment of GCA” eCRF page. Field “Has the patient flared since their last visit?” will be used to count the number of flares. Scheduled and unscheduled visits will be used.

8.2.4.1. Statistical Analysis

Number of flares and subjects with at least one flare from Baseline to the Week 52 visit will be summarized by treatment group over time. Cumulative number of flare at the Week X visit is the cumulative number of flare between Baseline and the Week X visit

8.2.5. Proportion of Subjects Requiring Hospitalizations for Disease Flare and Number of Hospitalizations for Disease Flare over Time

The hospitalizations for disease flare will be identified through the adjudication of AESI, and will include events from the following category: “Severe Flare including Hospitalizations”.

8.2.5.1. Statistical Analysis

Number of hospitalizations for disease flare and subjects with at least one hospitalization for disease flare from first SC IP to the Week 52 visit, will be summarized by treatment group over time

8.3. Other Efficacy Endpoints

No handling rule for missing data will be done in [Section 8.3](#), apart from the specific rules detailed within each sub-section.

8.3.1. Patient and Physician-Reported Outcomes

The following summaries on Patient and physician-reported outcomes will be performed on the ITT set except for the HAQ-DI which is only filled out for subjects with symptoms of PMR. Therefore, summaries of the HAQ-DI will be performed on the subset of ITT subjects who are indicated to have symptoms of PMR at screening.

If the date of result does not match the scheduled visit date, a visit mapping will be applied. A result will be mapped to Visit Week X if it occurs +/- 14 days to visit X.

8.3.1.1. Patient’s and Physician’s Global Assessment (PGA) of Disease Activity

The PtGA and PhGA of disease activity will be recorded on a 10 cm visual analogue scale (VAS) and will be conducted at each visit.

The PtGA asks “Considering all of the ways your condition has affected you, how do you feel today?” and uses a 10 cm VAS with anchors 0 (“very well”) to 10 (“very poor”).

The PhGA asks “What is your assessment of the patient's current disease activity?” and uses a 10 cm VAS ranging from 0 (“none”) to 10 (“extremely active”).

For both endpoints, a negative change from baseline reflects an improvement, and a positive change from baseline reflects a worsening.

The scores and change from Baseline will be summarized by treatment and visit.

All PtGA and PhGA data will be listed separately.

8.3.1.2. Patient Global Impression of Change (PGIC)

Patient-reported response to treatment will be assessed using the Patient Global Impression of Change (PGIC) measure, a single item completed by subjects to provide a clinically meaningful

summary of an individual's response to treatment. The assessment provides an estimate of the magnitude of treatment response at different time points during the study. Responses include: Much Better, Better, Slightly Better, No Change, Slightly Worse, Worse, and Much Worse.

The categorical data of subject rating of change will be summarized by treatment group, visit and response category.

All PGIC data will be listed.

8.3.1.3. Pain Numeric Rating Scale

The assessment of pain severity will be made using a single pain severity item on which subjects will be asked to rate the severity of their average pain now on an 11-point numeric rating scale ranging from 0, "no pain" to 10, "the worst pain imaginable".

The pain NRS and change from Baseline will be summarized by treatment group and visit. A negative change from baseline in pain NRS reflects an improvement in pain, and a positive change from baseline reflects a worsening in pain.

All pain NRS data will be listed.

8.3.1.4. Health Assessment Questionnaire – Disability Index (HAQ-DI)

The HAQ-DI indicates the extent of the subject's functional ability during the past week, and will be assessed for the subgroup of subjects with symptoms of PMR. Only subjects with the "Symptoms of PMR" answered to "Yes" at screening (GCA Diagnosis form) will be included in the analysis of the HAQ-DI.

The HAQ-DI consists of 20 questions in 8 categories of functioning – dressing and grooming, arising, eating, walking, hygiene, reach, grip, and usual activities.

Each functional area contains at least two questions. For each question, there is a 4-level difficulty scale that is scored from 0 to 3, representing "no difficulty" (0), "some difficulty" (1), "much difficulty" (2), and "unable to do" (3).

In addition to assessing functional ability during the past week, the questionnaire asks if any aids or devices are needed for any of the activities. When aids or devices are indicated by a subject and if the unmodified score is 0 or 1, then the score will be raised to 2.

The aids and devices are assigned to the specific HAQ sections as follows:

- Dressing and Grooming: Devices used for dressing (button hook, zipper pull, shoe horn, etc.)
- Arising: Special or built-up chair
- Eating: Built-up or special utensils
- Walking: Cane, walker, crutches, wheelchair
- Hygiene: Bathtub bar, long-handled appliances in bathroom, raised toilet seat
- Reach: Long-handled appliances for reach
- Grip: Jar opener for jars previously opened
- When "Other" is ticked, all functions recorded on the same eCRF page will be raised to 2

There are no specific aids and devices assigned to usual activities.

The score for each of the 8 category scores is taken as the maximum score given to the related questions. If no questions within a given functional area were answered, no score will be provided for that category (even if answers on aids or equipment are available).

EXAMPLE:

If a subject answers as follows for the Dressing and Grooming category:

Q. Are you able to dress yourself, including tying shoelaces and doing buttons?

Answer: without any difficulty → Score = 0

Q. Are you able to shampoo your hair?

Answer: with some difficulty → Score = 1.

The score for the Dressing and Grooming category would be 1. However, if devices used for dressing (button hook, zipper pull, shoe horn, etc.) are indicated then the score for the Dressing and Grooming category would be raised to 2.

The average of these non-missing functional area scores defines the continuous HAQ-DI score ranging from 0 to 3, with higher scores indicating worse disability. If there are less than 6 functional area scores available, no imputation will be done and the HAQ-DI will be set to missing for the according assessment.

Absolute and change from baseline in HAQ-DI score will be summarized by treatment group and visit. A negative CBF reflects an improvement in functional disability

All HAQ-DI data will be listed: Raw scores; aids and devices used; help from another person; and derived scores.

8.3.1.5. Functional Assessment of Chronic Illness Therapy-Fatigue (FACIT-Fatigue)

The FACIT-Fatigue is a 13-item questionnaire formatted for self-administration that assesses subject reported fatigue and its impact upon daily activities and function over the past seven days. Specifically, subjects are asked to answer each question using a 5-point Likert-type scale (4 = Not at all; 3 = A little bit; 2 = Somewhat; 1 = Quite a bit; and 0 = Very Much). Each of the 13 items of the FACIT-Fatigue Scale ranges from 0-4, with a range of possible total score from 0-52, with 0 being the worst possible score and 52 the best (i.e. less fatigue). Scores below 30 indicate severe fatigue. To obtain the 0-52 score each negatively-worded item response is recoded so that 0 is a bad response and 4 is good response. All responses are added with equal weight to obtain the total score. The total score is calculated as the sum of all the individual items after recoding some of the items. Recoded items are displayed in **Table 5** with a “-” sign.

Table 5 FACIT-Fatigue Question Reversal

Item Number	Reverse Item?	
1	4	-
2	4	-
3	4	-
4	4	-
5	4	-
6	4	-
7	0	+
8	0	+
9	4	-
10	4	-
11	4	-
12	4	-
13	4	-

If more than 50% of the items are answered (i.e. if at least 7 questions are answered), the scores will be pro-rated: [Sum of item scores] x [N of items in the questionnaire: 13] / [N of items answered]. If less than 50% of the items are answered, no imputations will be done and the score will be considered as missing.

EXAMPLE

If a subject responds to 10 questions and the total score for these 10 questions is 22 then Total score will be:

$$\text{TOTAL_Score} = (22 \times 13) / 10 = 28.6$$

Absolute and change from baseline in FACIT-Fatigue following endpoints will be summarized by treatment group and visit. A negative CFB reflects an improvement in fatigue

All FACIT-Fatigue data will be listed.

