#### **7.4.4. Functional Assessment of Chronic Illness Therapy-Fatigue (FACIT-Fatigue)**

The FACIT-Fatigue is a questionnaire that assesses self-reported tiredness, weakness, and difficulty conducting usual activities due to fatigue [Cella, 2002; Yellen, 1997]. The total FACIT-Fatigue score ranges from 0 to 52, with a higher score indicating less fatigue.

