3.4. Dose Adjustment/Modifications

No dose adjustment of sirukumab will be allowed in this study.

4. General Statistical Considerations

All analyses detailed in this SAP will be conducted using Statistical Analysis System (SAS)[®] statistical analysis software version 9.3 or higher (SAS Institute, Inc., Cary, North Carolina, USA). All SAS programs used to generate analytical results will be developed and validated according to PPD SAS programming standards and validation procedures.

Summary data will be presented in tabular format by treatment. Continuous variables will be summarized by descriptive statistics including number of subjects (N), mean, standard deviation (SD), median, minimum, and maximum.

Mean and median will be displayed to 1 more decimal place than the measured value. The SD will be displayed to 2 more decimal places than the measured value. Minimum and maximum will be displayed to the same decimal place as the measured value.

Categorical data (such as sex) will be summarized by number and percentage of subjects in each category. Percentages will be suppressed when the count is zero. A row denoted “Missing” will be included in count tabulations where necessary to account for missing values. The denominator for all percentages will be the number of subjects within the treatment (randomized or actual) group for the analysis set of interest, unless otherwise specified. Percentages which differ from 100% will be presented to 1 decimal place and 100% will be presented without a decimal.

Change from Baseline is the post-baseline value minus the baseline value. If the baseline or post-baseline value is missing, then the change from baseline is set to missing. For each scheduled post-baseline time point where change from Baseline is evaluated for continuous variables, descriptive statistics will be displayed for the values at Baseline, values at the scheduled post-baseline time point, and values for change from Baseline at the scheduled post-baseline time point for the set of subjects who have data at both Baseline and the time point being assessed. Early withdrawal visits as well as 16-week follow-up visits are considered as scheduled visits.

In case of multiple assessments for a scheduled visit, the last non missing assessment for this visit will be used for the summaries over time. All results will be listed.

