8.3.1.8. EuroQoL-5Dimensions, 5 Levels

EQ-5D essentially consists of 2 elements: the EQ-5D descriptive system and the EQ visual analogue scale (EQ VAS).

The EQ-5D descriptive system comprises the following 5 dimensions:

- Mobility
- Self-Care
- Usual Activities
- Pain/Discomfort
- Anxiety/Depression

Each of these 5 dimensions has 5 levels: 1: no problems; 2: slight problems; 3: moderate problems; 4: severe problems; 5: Unable to do.

The digits for each of the 5 dimensions can be combined in a 5-digit number describing the subject's health state: e.g. state 11111 indicates no problem on any of the 5 dimensions, while state 12345 indicates no problems with Mobility, slight problems with Self-Care, moderate problems with doing Usual Activities, severe Pain or Discomfort and extreme Anxiety or Depression. A total of 3125 possible health states is defined, therefore the health states will not be summarized. Instead, the health states will be converted into a single summary index (EQ-5D Index) by applying a formula that attaches weights to each of the levels in each dimension. The weights based from the UK population will be used for the conversion, regardless of the origin country of the subject.

In order to create the EQ-5D Index (Utility Index), the conversion provided from the "EQ-5D-5L Crosswalk Index Value Calculator" Excel file will be used. This file is downloadable from: http://www.euroqol.org/fileadmin/user_upload/Documenten/Excel/Crosswalk_5L/EQ-5D-5L_Crosswalk_Index_Value_Calculator.v2.xls. [Van Hout B, Janssen MF, et al.]. The "UK" column of the "EQ-5D-5L Value Sets" sheet will be used for the conversion.

The EQ VAS records the subject's self-rated health on a 20-cm vertical VAS where the endpoints are labelled 'best imaginable health state' (score of 100) and 'worst imaginable health state' (score of 0). The EQ VAS can be used as a quantitative measure of health outcome as judged by the individual subjects.

The following endpoints will be summarized by treatment group and visit:

- Absolute and change from baseline in EQ-5D index (Utility Index)
- Absolute and change from baseline in EQ-5D VAS

For both changes from baseline, a negative change indicates an improvement, and a positive change indicates a worsening.

All EQ-5D-5L data (raw and derived) will be listed. Conversion between each of the 5-digit numbers and associated weight will be listed.

9. Safety Analyses

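### The SAP signs improvement the wrong way for FACIT-Fatigue and the EQ VAS, and its printed FACIT response key does not yield the stated 0-worst, 52-best total

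*SAP*

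**What the plan says.** **Change score.** SAP Section 4 (General Statistical Considerations) sets one definition for all continuous endpoints: "Change from Baseline is the post-baseline value minus the baseline value".

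**FACIT-Fatigue scale.** SAP Section 8.3.1.5 describes a 0 to 52 total "with 0 being the worst possible score and 52 the best (i.e. less fatigue"), and treats totals under 30 as severe fatigue. Protocol Section 7.4.4 agrees: 0 to 52, "with a higher score indicating less fatigue".

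**FACIT-Fatigue direction.** The same SAP section closes with "A negative CFB reflects an improvement in fatigue".

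**FACIT-Fatigue item coding.** The SAP says "subjects are asked to answer each question using a 5-point Likert-type scale", and prints the key as "4 = Not at all; 3 = A little bit; 2 = Somewhat; 1 = Quite a bit; and 0 = Very Much". It then says "each negatively-worded item response is recoded so that 0 is a bad response and 4 is good response". Table 5 marks 11 items (1 to 6 and 9 to 13) as 4 minus the response, and items 7 and 8 as 0 plus the response, that is, left alone.

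**EQ-5D.** SAP Section 8.3.1.8 anchors the EQ VAS at 100 for the best state and 0 for the worst. It then says of the EQ-5D index and the VAS together: "For both changes from baseline, a negative change indicates an improvement, and a positive change indicates a worsening".

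**The concern.** The direction sentences tell the reader how to interpret the change tables. For FACIT-Fatigue and the EQ VAS they contradict the scale defined a few lines earlier, so an arm whose patients improve would be read as one that declined.

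No SAP-wide sign convention explains this. Calling a negative change an improvement is right for the patient and physician global assessments, the pain scale and HAQ-DI, where the SAP makes high scores bad. For the SF-36v2 summary scores, where high is good, the SAP correctly makes a positive change the improvement. FACIT-Fatigue and the EQ VAS are the exceptions.

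The item coding is a separate matter, because it can alter the derived FACIT total and not only its label. The printed key already gives 4 to Not at all. If those are the codes as collected, subtracting 11 of them from 4 undoes the intended orientation, and items 7 and 8 are left running backwards.

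**Working it through.** **1. Direction of change**

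Inputs: the definition of change (SAP Section 4), the FACIT range (SAP 8.3.1.5; Protocol 7.4.4) and the EQ VAS anchors (SAP 8.3.1.8).

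| Measure | Best score | Illustrative improvement | Change | SAP label for that sign |
|---|---|---|---|---|
| FACIT-Fatigue | 52 | 20 to 40 | 40 − 20 = +20 | worsening (implied) |
| EQ VAS | 100 | 50 to 70 | 70 − 50 = +20 | worsening (stated) |
| SF-36v2 summary scores | higher | any gain | positive | improvement |

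The first two labels are reversed and the third is right. The documents do not state the direction of the EQ-5D index. On the assumption that a higher utility is better, its label is reversed too.

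**2. FACIT item coding**

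Let *k* be the strength of endorsement, from 0 (Not at all) to 4 (Very much). Best health is *k* = 0 on the 11 reversed items and *k* = 4 on items 7 and 8; worst health is the opposite. The documents do not print the item wording. That items 7 and 8 are positively worded is inferred from the recoding rule and Table 5.

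- *Intended total* = Σ₁₁(4 − *k*) + Σ₂*k*. Best: 11×4 + 2×4 = 52. Worst: 0. This reproduces the SAP's stated scale.
- *Reading A:* the printed key is the raw code for every item (*r* = 4 − *k*), and Table 5 is then applied. The 11 items give 4 − *r* = *k*; items 7 and 8 give 4 − *k*. Best: 11×0 + 2×0 = 0. Worst: 11×4 + 2×4 = 52. Adding the intended and reading A totals item by item gives 13×4 = 52, so reading A is always 52 minus the intended total.
- *Reading B:* the printed key is the final code for every item, with no further reversal. Best: 11×4 + 2×0 = 44. Worst: 11×0 + 2×4 = 8.
- *Reading C:* the printed key shows the 11 items after recoding, and items 7 and 8 use the opposite key. Best 52, worst 0, as stated. The SAP does not say that this is meant.

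**3. How the two faults interact**

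Take a patient who moves from Quite a bit to A little bit on the 11 items, and from A little bit to Quite a bit on items 7 and 8.

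| Scoring | Baseline | Follow-up | Change |
|---|---|---|---|
| Intended (also reading C) | 11×1 + 2×1 = 13 | 11×3 + 2×3 = 39 | +26 |
| Reading A | 52 − 13 = 39 | 52 − 39 = 13 | −26 |
| Reading B | 11×1 + 2×3 = 17 | 11×3 + 2×1 = 35 | +18 |

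Under reading A the direction sentence fits the change, but the absolute scores shown beside it are inverted against the 52-best scale. Under the intended scoring, and in this example under reading B, the sentence is wrong.

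**4. The SAP's pro-rating example**

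Ten answered items with a subtotal of 22 give 22 × 13/10 = 28.6, which matches the SAP. If 22 is the intended subtotal, reading A turns it into 40 − 22 = 18, and 18 × 13/10 = 23.4.

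**The case against.** The direction contradiction has no good answer: nothing elsewhere in either document corrects it. The stronger objections concern coding and impact.

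*The readings are not equally plausible.* The SAP fixes its target twice, by the 52-best scale and by the rule that 4 must be a good response after recoding. Reading A breaks that rule and reading B ignores Table 5. Only reading C, or raw codes starting at 0 for Not at all, satisfies everything else in the section. This is fair as far as it goes: the count of readings is not a probability, and no mis-scored total has been shown. Even so, a programmer who applies the printed key to every question and then applies Table 5 gets an inverted total, and nothing in the text says not to.

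*The proposed raw key is not in the documents.* True. It is inferred as the key that fits Table 5, the recoding rule and the 52-best total together, and the two test records would expose a mismatch with the codes as collected.

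*The effect is small.* This largely stands. The sentences drive no computation. The SAP plans no efficacy testing after termination, Part B patient-reported outcomes are only listed, no planned output uses the under-30 cut-off, and the underlying data are listed. But these are listed secondary endpoints, and with no tests the sign of the summarised change carries the interpretation.

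*Programs must be validated anyway.* Validation against an ambiguous specification does not settle which key is meant.

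**Conclusion.** The concern holds. Two direction sentences are wrong as written, for FACIT-Fatigue and for the EQ VAS; this follows from the SAP's own definitions with no outside source. For the EQ-5D index the error is inferred, on the assumption that higher utility is better.

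The FACIT key is also defective as written. Best and worst health score 52 and 0 as intended, 0 and 52 if the key is raw for all items, and 44 and 8 if it is final for all items. This part assumes that items 7 and 8 are positively worded.

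No reading makes the whole FACIT section consistent: either the total departs from the stated scale, or the direction sentence is wrong. The consequence is limited to the interpretation, and possibly the derivation, of Part A descriptive summaries. No test or responder rule changes.

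**What to change.** Correct the FACIT key and direction sentence together. If the program follows reading A, reversing the sentence alone would mislabel the change.

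- **SAP 8.3.1.5:** state raw coding as 0 = Not at all to 4 = Very much, keep Table 5, and say that a positive change is an improvement in fatigue.
- **SAP 8.3.1.8:** say that a positive change in the EQ VAS is an improvement and a negative change a worsening. Apply the same wording to the EQ-5D index once the direction of the value set is confirmed.
- **Program check:** score one all-best FACIT record (Not at all on the 11 reversed items, Very much on items 7 and 8), which should total 52, and one all-worst record, which should total 0.

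The cost is two sentences, one coding line and two test records, with no new data or analysis.
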